7.3.5 Occurrence of TEEs

All TEEs (thrombotic, embolic, or thromboembolic events) must be recorded in the source data and reported as SAEs within 24 hours. If TEEs are suspected, appropriate examinations according to local standards (e.g. Doppler scan using color duplex, X-ray, CT scan) should be obtained and documented. Therapeutic measures for managing TEEs shall be initiated according to local clinical practice (e.g., anticoagulation).

As a component of the assessment of AEs, the Investigator will also be questioned regarding the occurrence of TEEs. These are defined according to the Standardized Medical Dictionary for Regulatory Activities (MedDRA) query “Embolic and thrombotic events”.

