5.6 Blinding, Emergency Envelopes and Breaking the Study Blind

This is a partially blinded randomised study, with patients and outcome assessors blinded to treatment allocation. Given the physical differences in the products and the emergency nature of the intervention, attending clinicians will not be blinded to the treatment. Thus, breaking the study blind is not an issue in this study.

The random allocation schedule will be prepared by a biostatistician not involved in the conduct of the trial (see **Section 9.3**). To minimise bias, neither the individual randomising nor any of the health care providers will know which treatment will be assigned to a given patient when coagulation factor replacement is ordered. Blood products will be transported to the OR in weighted temper-proof boxes to maintain the blind until IMP infusion.

The type of IMP administered will be recorded in a manner that will not unblind the outcome assessor. Patients will also be blinded to treatment allocation.

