5.7 Treatment Compliance

5.7.1 Drug Dispensing and Accountability

A drug dispensing log and the inventory will be kept current by the Investigator, detailing the dates and quantities of *Octaplex* administered to each patient. The inventory and the drug dispensing log will be available to the monitor to verify drug accountability during the study. Used or partially used vials are to be destroyed at the site. Any unused *Octaplex* either not dispensed or returned from the operating room or the ICU will be accounted for. After the Sponsor has granted written approval of destruction, these can be destroyed either at the study site or returned to the depot for destruction. Destruction can be initiated only after accountability has been verified and fully reconciled by the monitor.

FP assigned to the study and dispensed accordingly will be tracked in an IMP FP dispensing log which will be available to the monitor to verify drug accountability during the study. FP returned unused from the operating room or the ICU will be handled according to the local practice.

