7.3.2.2 Collection of AEs

The condition of the patient will be monitored throughout the study. At each visit, whether scheduled or unscheduled, AEs will be elicited using a standard non-leading question such as "How have you been since the last visit/during the previous study period?" In addition, the Investigator/blinded outcome assessor will check the patient records for any documented event.

Any AE or ADR which occurs during the study will be noted in detail on the appropriate pages of the CRF. If the patient reports several signs or symptoms representing a single syndrome or diagnosis, the diagnosis should be recorded in the CRF. The Investigator will grade the severity of all AEs or ADRs (mild, moderate or severe), the seriousness (non-serious or serious) and the causality as defined below. The Sponsor is responsible for assessing the expectedness of each ADR (expected or unexpected) as defined below.

In the event of clinically significant abnormal laboratory findings, the tests will be confirmed and the patient followed up until the laboratory values have returned to normal and/or an adequate explanation for the abnormality has become available.

Diseases, signs and symptoms and/or laboratory abnormalities already present before the first administration of IMP will not be considered AEs unless an exacerbation in intensity or frequency (worsening) occurs.

The Investigator will provide detailed information about any abnormalities and about the nature of and reasons for any action taken, as well as any other observations or comments that may be useful for the interpretation and understanding of an AE or ADR.

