9.2.3.1 Adverse events, including thromboembolic and other events of special interest

AEs will be coded according to the latest Medical Dictionary for Regulatory Activities (MedDRA) version as specified in the Data Management Plan. The analysis will focus on treatment-emergent adverse events (TEAEs), i.e., AEs that started or worsened after start of infusion with IMP.

All TEAEs, related TEAEs (i.e., AEs unlikely, probably or possibly related to the IMP) and serious TEAEs will be summarised and tabulated according to primary system organ class and preferred term. TEAEs leading to death and TEAEs resulting in withdrawal from the study will be tabulated using frequency tables if a reasonable number of events of this type are observed.

Analogous frequency tables for TEEs (identified using MedDRA SMQs) and composite events will be provided separately.

Patient listings will be provided for patients with SAEs, TEEs, AEs leading to withdrawal from the study and AEs leading to death. Listings for non-treatment-emergent AEs, e.g., for patients enrolled but not randomised will be provided separately.

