### 11.1. Adverse events

AEs will be coded according to the MedDRA. Coding will be agreed upon with the Sponsor before database lock (cf. DMP).

All AEs recorded for patients in the SAF will be listed in the appendix of the study report, differentiated by treatment-emergent and non-treatment-emergent AEs.

Only treatment-emergent AEs (TEAE) will be analysed, i.e., all new and worsening pre-existing AEs occurring after first IMP administration up to POD-30. It is assumed that for each increase in intensity of an AE a new entry of the AE will be recorded by the investigator; hence, such cases will be analysed like different phases of the same AE.

A descriptive analysis will be performed. This analysis will comprise the following set of tables, separated by treatment group and time of first occurrence (within 48 hours, 7 days and 30 days post-surgery):

- Global incidence
- Incidences by primary system organ classes (SOC) and incidences of preferred term within primary SOC sorted according to the Internationally Agreed Order

Global incidences of primary SOC and preferred terms will be calculated for

- All TEAE irrespective of the causality assessment
- TEAE by relationship (probable, possible, unlikely, not related and unclassified)
- TEAEs by worst severity
- Serious TEAEs
- TEAEs possibly or probably related per PI assessment
- TEAEs possibly or probably related per sponsor assessment
- TEAEs possibly or probably related per PI and/or sponsor assessment
- TEEs per PI assessment
- TEEs per MedDRA SMQ
- TEEs per sponsor assessment
- Treatment-emergent major adverse cardiac events (MACE)

Multiple counts within a preferred term or SOC (repeated or different included terms or changes in descriptors) will be counted only once for the calculation of incidences.

A listing of 'special cases' containing patient ID, age, sex, AE descriptors and start and end of treatment will be prepared for the following types of TEAEs:

- Fatal SAEs
- AEs which led to discontinuation
- Myocardial infarction
- Stroke
- Acute liver injury
- Acute kidney injury
- TEEs
- MACE
- TRALI
- TACO

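### Thromboembolic events are recognised by an Investigator not stated to be blinded, and no blinded classification is required, so their comparison within safety endpoint 1 is open to assessment bias

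*Protocol*

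**What the plan says.** On who is blinded, Protocol 5.6 says: "This is a partially blinded randomised study, with patients and outcome assessors blinded to treatment allocation". It adds that attending clinicians are not blinded and that the product type is recorded so as to keep the assessor blind. The Investigator is not mentioned there.

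On finding and grading events, Protocol 7.3.2.2 says that "the Investigator/blinded outcome assessor will check the patient records for any documented event", and then: "The Investigator will grade the severity of all AEs or ADRs (mild, moderate or severe), the seriousness (non-serious or serious) and the causality". No blinding condition is attached to either task.

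On TEEs, Protocol 7.3.5 says: "As a component of the assessment of AEs, the Investigator will also be questioned regarding the occurrence of TEEs". It defines TEEs by a standard MedDRA query (SMQ), calls for examinations to local standards when a TEE is suspected, and requires every TEE to be reported as an SAE within 24 hours.

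On access to allocation, Protocol 5.7.1 says: "A drug dispensing log and the inventory will be kept current by the Investigator, detailing the dates and quantities of" Octaplex given to each patient.

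On analysis, Protocol 9.2.3.1 says: "Analogous frequency tables for TEEs (identified using MedDRA SMQs) and composite events will be provided separately". SAP 11.1 lists three TEE tabulations: "TEEs per PI assessment", one by the SMQ and one by sponsor assessment. It does not say whether the sponsor's assessment is made blind, or which tabulation is the TEE part of safety endpoint 1.

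**The concern.** Protocol 1.1 acknowledges that PCC at high doses may carry a higher thrombotic risk, and 1.3 presents the dose cap as mitigation. TEEs are therefore a harm on which a reader will want an unbiased comparison. The trial has a blinded outcome assessor and takes steps to protect that blind, yet it does not clearly use the assessor for this outcome.

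Whether a TEE is recognised depends partly on judgement. Work-up starts from suspicion, there is no scheduled screening, and local standards apply. Someone who knows that the patient received PCC may look harder for thrombosis, or may explain a borderline finding another way. Either would move the TEE comparison. The seriousness of non-TEE events, which also enters safety endpoint 1, is graded by the same role.

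**Working it through.** **Setting the sections side by side**

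1. *Is the Investigator blinded?* Protocol 5.6 names patients and outcome assessors only. The Investigator keeps the Octaplex log (5.7.1), is responsible for dispensing the product (13) and may personally approve each eCRF (8.1.2, which also allows a sub-investigator to do so). SAP 9 says that the eCRF holds every Octaplex or FP dose with its batch number. Neither document says in so many words that the Investigator knows the allocation, but these duties make it a strong inference.
2. *What does the blinded assessor do for adverse events?* Protocol 7.3.2.2 gives one task, the record check, joined to the Investigator by a slash. That could mean either person, both, or one role. Grading then goes to the Investigator alone.
3. *Is the seriousness of a TEE a judgement?* No. Under 7.3.5 every recognised TEE is an SAE. What stays open is whether an event is recognised and classified as a TEE.
4. *Does the SMQ remove the problem?* No. It sorts coded terms that sites have already reported, so an event missed or described differently at the site is missed or moved in the SMQ count too.
5. *Does the sponsor's assessment remove it?* Only if it is made without the allocation, which SAP 11.1 does not require.

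**How far the comparison could move**

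The plan gives no precision or power figure for TEEs, so there is none to reproduce. The inputs are:

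- TEE risk of 8% in both arms, a round figure between the pilot rates in Protocol 1.1 (7.4% PCC, 8.2% FP).
- 205 patients per arm, the minimum in Protocol 4.1.
- A shift of 2 events per 100 PCC patients. This is an assumption; the documents give no such figure.

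The results are:

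- Expected events per arm: 205 × 0.08 = 16.4.
- Observed risk ratio after the shift: 0.10 / 0.08 = 1.25, or 0.06 / 0.08 = 0.75.
- 95% CI half-width for the risk difference: 1.96 × √(2 × 0.08 × 0.92 / 205) = 0.0525, or 5.3 points.
- Shift relative to the half-width: 0.02 / 0.0525 = 38%.

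At the largest planned size (1000 evaluable, 500 per arm) the half-width is 1.96 × √(2 × 0.08 × 0.92 / 500) = 0.0336. The same shift is then 0.02 / 0.0336 = 59% of it. More patients narrow the interval but leave the bias where it is.

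A second illustration uses unequal ascertainment: observed RR = true RR × (sensitivity in PCC / sensitivity in FP). The sensitivities are again assumed, and the true RR is 1.

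| Sensitivity, PCC / FP | Observed RR |
|---|---|
| 0.95 / 0.85 | 1.12 |
| 0.90 / 0.70 | 1.29 |
| 0.85 / 0.95 | 0.89 |
| 0.70 / 0.90 | 0.78 |

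With a true risk of 7.4% to 8.2% and 205 per arm, this is a difference of about 1.5 to 3.4 events. The 95% CI for the risk ratio spans about a factor of 2 either way, so a bias of this size could not be detected from the results.

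**The case against.** The strongest reply is that the plan already has several safeguards. The blinded assessor is named in the record check. Every TEE becomes an SAE by rule, and suspected TEEs need documented examinations. TEEs have a standard MedDRA definition. All three SAP tabulations will be produced, so any disagreement between them will be visible. The safety analysis is descriptive, with no confirmatory test.

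Much of this stands, and it rules out several stronger readings that a reader might infer:

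- *That the blinded assessor has no part in finding events.* Protocol 7.3.2.2 names that role.
- *That the Investigator decides whether a TEE is serious.* Protocol 7.3.5 settles that once a TEE is recognised. Discretion over seriousness applies to other events.
- *That TEEs are the trial's main harm endpoint.* Six safety endpoints are listed without ranking, and TEEs are an example within the first.
- *That the Investigator is declared unblinded.* This is inferred from duties. Data entry can also be delegated (8.1.1). The text available here lacks Protocol 7.3.4 and 8.3, which may bear on roles; nothing is inferred from their absence.
- *That three tabulations amount to selective reporting.* The protocol uses the SMQ in both places where it defines or tabulates TEEs, and all three counts will be shown. Naming the headline count is mainly clarification.

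The safeguards still leave one gap. The PI and SMQ counts start from what the site chose to report, and the sponsor count may be made with the allocation in view. Agreement among the three would therefore not show that assessment bias is absent.

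**Conclusion.** The point holds for the recognition and classification of TEEs and, to a lesser degree, for the seriousness of other adverse events. Both rest with an Investigator who is not stated to be blinded and who holds allocation records, and no TEE classification is required to be made blind.

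The direction and size of any bias cannot be determined from the documents. The risk ratios of 0.75 to 1.29 above rest on assumed shifts and sensitivities. They show that modest differences in judgement matter when about 16 events per arm are expected; they are not evidence that bias will occur. The primary efficacy analysis is not affected.

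A reader might go further and infer that all severity and seriousness grading should move to the blinded assessor. The documents do not support that. They treat both as medical judgement by the Investigator and do not state the assessor's qualifications. A low-cost improvement to the TEE comparison is warranted, not a redesign of safety assessment.

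**What to change.** **Protocol 7.3.2.2 and 7.3.5.** Replace the slash with a clear assignment: the existing blinded outcome assessor does the record check and records TEE yes/no. State how the records that the assessor reads are kept free of product information, in line with 5.6. Leave severity, seriousness, causality and 24-hour SAE reporting with the Investigator. That way no second seriousness record arises that would need reconciling.

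**SAP 11.1.** Require the already planned sponsor TEE assessment to be made without sight of treatment allocation and completed before database lock. Keep the protocol's SMQ definition as the headline TEE count for safety endpoint 1. Present the blinded-assessor and blinded-sponsor counts beside it as the check on site-reporting bias, and label the PI count supportive.

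**Cost.** Wording in both documents, a few eCRF fields and some assessor time. The headline count would still rest on site-reported terms. The two blinded counts do not remove that dependence, but they let a reader see whether it matters.

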7.3.6 Laboratory Tests

The following laboratory parameters will be investigated during the study at the time points specified in **Section 6**.

7.3.6.1 Central Laboratory

No laboratory tests will be done at a central laboratory:

7.3.6.2 Local Laboratory

Table 6 summarises all test parameters performed as part of standard of care, the results of which will be collected as available.

Table 6 Test Parameters and Laboratories

Test	Material needed	Responsible Laboratory
Coagulation profile		
Point-of-care INR	Fresh blood	Local
(PT, aPTT, INR, fibrinogen activity via Clauss assay)	Citrated blood	Local
*ROTEM EXTEM CT	Citrated blood	Local
*ROTEM EXTEM MCF	Citrated blood	Local
*ROTEM FIBTEM MCF	Citrated blood	Local
PlateletWorks		
Haematology – standard panel as per local lab	Citrated blood	Local
Clinical chemistry – standard panel as per local lab	Serum	Local
Safety laboratory analyses		
Troponin	Serum	Local
ALT/ALP	Serum	Local
Bilirubin	Serum	Local
Creatinine	Serum	Local

ALT, alanine aminotransferase; ALP, alkaline phosphatase; CT, clotting time; MCF, maximum clot firmness; PT, prothrombin time; aPTT, activated partial thromboplastin time; ROTEM, thromboelastometry

*ROTEM or TEG can be measured

The haemoglobin and INR measurements will be performed at preestablished time points (**Table 7**).

Table 7 Mandatory Test Parameters and Laboratories

Test	Material needed	Responsible laboratory
Coagulation profile		
Point-of-care INR	Fresh blood Citrated blood	Local Local
Haematology		
Haemoglobin	Citrated blood	Local

Blood Sampling

All blood sampling will be performed as per standard practice at the local institution.

The *actual* time of blood sampling will be recorded. If the draw time is not recorded for samples processed in the laboratory, the draw time will be estimated based on the received time in the laboratory minus 10 minutes. For ROTEM and PlateletWorks, if the exact draw time is not recorded, the time for start of testing will be used for draw time.

Citrated and Fresh Blood

Citrated and fresh blood as required by the local laboratory will be collected and processed in accordance with local requirements.

Serum

Serum will be obtained for the determination of clinical chemistry, haematology, and safety labs (ALT, ALP, creatinine, bilirubin, troponin), where a serum blood sample has been collected.

Recording of Clinically Significant Abnormal Laboratory Values as AEs/ADRs

Other than abnormal laboratory values due to the underlying condition, the Investigator must assess the clinical significance of abnormal laboratory values outside the specified normal range. Any clinically significant abnormalities will be documented. All specified clinically significant abnormalities will be documented as AEs/SAEs and investigated.

Additional tests and other evaluations required to establish the significance or aetiology of specified abnormalities or to monitor the course of an AE will be obtained if clinically indicated. Follow-up will persist until resolution or up to the Study Completion Visit, whichever occurs first.

7.3.7 Other Relevant Safety Information

a) Post-study related safety reports

Proactive monitoring for post-study SAEs is not required.

In case a post-study SAE is identified, the Investigator should complete an SAE form and also state the relation to the clinical study in the report.

b) Pregnancies

Patients who are known to be pregnant will not be included in the study. In patients of reproductive age, pregnancy is ruled out prior to the cardiac surgery as part of standard of care.

Overdose, interaction, medication error and lack of efficacy

The following safety relevant information should be reported as AE or, if the reaction fulfils one of the criteria for seriousness, as SAE.

c) Drug overdose

An overdose is a deliberate or inadvertent administration of a treatment at a dose higher than specified in the protocol and higher than the known therapeutic dose that is of clinical relevance. The reaction must be clearly identified as an overdose.

d) Drug interaction

A drug interaction is a situation in which a substance or medicinal product affects the activity of an IMP, i.e., increases or decreases its effects, or produces an effect that none of the products would exhibit on its own. The reaction must be clearly identified as a drug interaction.

e) Medication error

A medication error involves the inadvertent administration or unintended use of a medicinal product which may be caused by the naming, presentation of pharmaceutical form/packaging or instructions for use/labelling. The reaction must be clearly identified as a medication error.

7.4 Appropriateness of Measurements

Since the ultimate goal of the study is the measure the need for post-therapy haemostatic interventions following cardiac surgery in adults, the clinical assessment of haemostatic effectiveness provides the key clinical information on treatment efficacy. Haemostatic effectiveness will be based on the haemostatic efficacy scale developed by Sarode and colleagues [69] (in discussion with the Food and Drug Administration), modified to reflect the special considerations of haemorrhage during cardiac surgery. The secondary and exploratory endpoints will provide further information on the clinical efficacy and safety of Octaplex in this clinical setting.

8 DATA HANDLING AND RECORD KEEPING

8.1 Documentation of Data

8.1.1 Source Data and Records

Source data are defined as all information related to clinical findings, observations or other activities in the study, written down in original records or certified copies of original records, allowing reconstruction and evaluation of the clinical study.

The Investigator will maintain adequate source records (e.g., case histories or patient files for each patient enrolled). Source records should be preserved as required by local regulations.

For each patient enrolled, the Investigator will indicate in the source record(s) that the patient participates in this study.

For data capture, a validated Electronic Data Capture (EDC) system providing an electronic CRF (eCRF) application will be used.

All data entered in the eCRF must be supported by source data in the patient records.

The Investigator will permit study-related monitoring, audit(s), IRB review(s) and regulatory inspection(s), by providing direct access to the source data/records.

The Investigator may authorise site staff (e.g., sub-investigators, clinical research coordinators/assistants, nurses) to enter study data into the eCRF. This must be documented in the Delegation of Authority Log signed by the Investigator.

8.1.2 Case Report Forms

Authorised study site staff (e.g., blood bank/pharmacy technologist, research coordinator/assistant) will be responsible for completing an eCRF record for each patient enrolled. All site personnel will be trained on completion of a patient's eCRF. The site is also provided with the approved eCRF Completion Guidelines which will assist in data entry and data issues/questions. Additional site training may be provided as refreshers throughout the study, if needed. All persons allowed to enter or to change eCRF data must be listed in the Delegation of Authority Log.

For each patient enrolled, an eCRF record will be completed within the EDC system and finally approved by the Investigator or an authorised sub-investigator.

Prior to operational use, the eCRF application will be validated. All site personnel will be trained on the EDC system and study specific eCRFs prior to receiving access to the live system for data entry.

